3.2.2 Assignment of Dosing Cohorts

Specific doses of rociletinib will be administered in combination with a fixed dose of MPDL3280A. Combination doses of rociletinib with MPDL3280A will be defined for each Dosing Cohort enrolled during the Dose Finding Phase, and currently two potential Dosing Cohorts are planned (see Table 5). The first Dosing Cohort will be 500 mg BID rociletinib and 1200 mg MPDL3280A on Day 1 of each 21-day cycle. At minimum, 3 patients will be enrolled into this cohort. If this combination dose is determined to be safe and tolerable, no further dose modifications for either drug will be made. Based on emerging safety and evaluable PK and/or pharmacodynamics data, the CSC may evaluate additional doses or schedules of rociletinib.

Cohort	Rociletinib Dose	MPDL3280A Dose
1	500 mg PO BID	1200 mg IV every 3 weeks
-1	375 mg PO BID	Day 1 of each 21-day cycle

Table 5:Phase 1 Dosing Cohorts

BID, twice daily; IV, intravenous; PO, oral.

A modified toxicity probability interval (mTPI) method (Appendix H) will be used to guide decisions on assignment of patients to different Dosing Cohorts. Compared with the 3+3 design, the mTPI method reduces the risk of exposing patients to doses above the MTD, which is defined as the acceptable daily oral dose with estimated probability of toxicity closest to 33%. The mTPI design is a model-based approach that has a pre-specified decision matrix that recommends escalating, reducing or maintaining the same dose or stopping dose escalation, based on the number of DLTs observed in the dose level under evaluation. Consequently, patients enrolled into the trial can be allocated to appropriate doses without conducting additional computations.

At each dose level, after the first evaluable 3 patients have completed Cycle 1, the CSC will meet to evaluate the Dosing Cohort data and to make a decision on the next step for Dosing Cohort assignment (increase dose, decrease dose, maintain same dose, or stop), which will be guided by the mTPI decision table (Appendix H). A patient will be deemed evaluable for safety and DLT determination if they have received at least 75% of the planned total dose of each drug within Cycle 1. Patients who receive <75% of the planned total dose of either rociletinib or MPDL3280A for reasons other than study drug-related AEs will not be included in the evaluation of the Dosing Cohort and will be replaced. If the dose is maintained, up to an additional 6 patients may be enrolled at the same dose, and the next safety evaluation will take place after all patients have completed Cycle 1. The CSC may decide to meet at any time to evaluate a Dosing Cohort if a safety signal arises or other data become available to justify re-evaluation of the Dosing Cohort before it is fully enrolled.

The enrollment/evaluation process will continue until at least 6 patients have been treated at any single dose level or enrollment of the maximum sample size of 18 patients for the Phase 1 portion of this study has been achieved.

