10.2.5 Safety Analyses

The safety analyses will be performed using the safety population.

Safety data analysis will be conducted on all patients receiving at least one dose of rociletinib or MPDL3280A. The number and percentage of patients experiencing one or more AEs will be summarized by dose level group, relationship to study drug, and severity. AEs will be coded using MedDRA terminology. Listings of patients who experienced DLT during Cycle 1, dose reductions, dosing interruptions, withdrawal due to an AE, SAEs and/or death will be presented. Laboratory parameters will be summarized using descriptive statistics, by post-dosing shifts relative to baseline, and data listings of clinically significant abnormalities. Vital signs, ECOG performance status, and ECG data will be summarized by changes from baseline values at each dose level using descriptive statistics.

A mTPI method will be used to identify the MTD or MAD and the RP2D. The mTPI, a model-based approach that has a pre-specified decision matrix that recommends escalating, reducing or maintaining the same dose or stopping dose escalation, based on the toxicities observed in the dose level under evaluation, reduces the risk of exposing patients to doses above the MTD compared with 3+3 design in which there is a 71% chance of escalation if the true but unknown rate of DLT is 20% and less than 50% chance of escalation if the true but unknown rate of DLT is higher than 30%.

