Appendix H: The Modified Toxicity Probability Interval (mTPI) Method

The modified toxicity probability interval methodology is described in detail in Ji et al, 2010, and Ji et al, 2013. A short summary is given below.

Dose-finding method:

The mTPI design employs a simple beta-binomial hierarchical model. Decision rules are based on calculating the probability of three outcomes corresponding to underdosing, proper dosing, and overdosing in terms of toxicity.

Consider d dose levels of a certain cytotoxic drug in a phase 1 trial. Let pi be the unknown probability of toxicity associated with the i-th dose, $I = 1, \ldots, d$. The toxicity probability usually increases with the dose level, so we assume $p_1 < p_2 < \ldots < p_d$. Suppose that dose i is currently used for treating patients and n_i ($n_i \ge 1$) patients have been treated at this dose. Suppose x_i ($x_i \le n_i$) patients experienced toxicity. Based on the observed values of x_i and n_i , we assume that physicians choose one of the following three decisions:

- 1. de-escalate (D) to the next lower dose (i-1);
- 2. stay (S) at the same dose i; or
- 3. escalate (E) to the next higher dose (i+1).

Depending on the decision, the next cohort is treated at dose j which can be one of the 3 doses $\{i-1, i, i+1\}$; the values of x_j and n_j are then observed for the new cohort, and an appropriate decision is chosen once again. The trial thus proceeds with the next cohort.

These additional rules are important for practical concerns:

- Safety rule 1 (early termination): Suppose that dose 1 has been used to treat patients. If there is greater than a 95% probability that toxicity with dose 1 is greater than the target toxicity level (33%), then terminate the trial due to excessive toxicity.
- Safety rule 2 (dose exclusion): Suppose that the decision is E, to escalate from dose i to (i+1). If there is greater than 95% probability that toxicity with dose i+1 is greater than the target toxicity level (33%), then treat the next cohort of patients at dose i and exclude doses (i+1) and higher from the trial, that is, these doses will never be used again in the trial.
- At the end of the trial, select as the MTD, the dose with the estimated probability of toxicity closest to 33%.

Implementation of the mTPI in Study CO-1686-018:

The decision table for escalating, reducing or maintaining the same dose is based on algorithm provided by Ji et al, 2010, with the following 3 inputs:

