- 1. Maximum of 14 patients treated at any dose
- 2. Target toxicity probability of 33%
- 3. Equivalence interval of 5% so that any dose with an estimated probability of toxicity in the interval [28%, 38%] can be selected as the MTD

References:

Ji Y and Wang S-J. Modified Toxicity Probability Interval Design: A Safer and More Reliable Method Than the 3+3 Design for Practical Phase 1 Trials. J Clin Oncol 2013;31:1785-91.

Cohort Decision Table

Number of patients treated at current dose

	1	2	3	4	5	6	7	8	9	10	11	12	13	14
0	Е	Е	Е	E	Е	Е	Е	Е	Е	E	E	Е	Е	Е
1	D	S	S	S	S	Е	Е	Е	Е	Е	Е	Е	Е	E
2		DU	D	S	S	S	S	S	S	Е	Е	Е	Е	E
3			DU	DU	D	S	S	S	S	S	S	S	S	S
4				DU	DU	DU	D	S	S	S	S	S	S	S
5					DU	DU	DU	DU	D	S	S	S	S	S
6						DU	DU	DU	DU	DU	D	S	S	S
7							DU	DU	DU	DU	DU	DU	D	S
8								DU						
9									DU	DU	DU	DU	DU	DU
10										DU	DU	DU	DU	DU
11											DU	DU	DU	DU
12												DU	DU	DU
13													DU	DU
14														DU
	г										7			

E = Escalate to the next higher dose S = Stay at the current dose D = De-escalate to the next lower dose U = The current dose is unacceptably toxic MTD=33% Sample size = 14

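### The claim that the mTPI lowers the risk of dosing above the MTD relative to 3+3 is not borne out by this protocol's table: with looks at 3 and 6 patients it escalates equally often and keeps an over-toxic dose more often

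*Combined protocol and SAP*

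**What the plan says.** Section 3.2.2 introduces the dose-finding rule with a comparative safety statement: "Compared with the 3+3 design, the mTPI method reduces the risk of exposing patients to doses above the MTD". It defines the MTD as the acceptable dose with "estimated probability of toxicity closest to 33" percent. Section 10.2.5 repeats the claim and attaches figures to it: the mTPI "reduces the risk of exposing patients to doses above the MTD compared with 3+3 design in which there is a 71% chance of escalation" at a true DLT rate of 20%, and a chance below 50% when the rate is above 30%. Both figures describe the 3+3. No corresponding figure is given for the mTPI, in either section or in Appendix H.

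Appendix H lists the inputs to the table: "Target toxicity probability of 33" percent, "Equivalence interval of 5" percentage points either side (28% to 38%), and "Maximum of 14 patients treated at any dose". One of its codes is "S = Stay at the current dose". The implementation paragraph there carries another study's number (CO-1686-018).

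Section 3.2.2 sets the first review after 3 evaluable patients. It allows up to 6 more if the dose is maintained, and it ends the process once at least 6 patients have been treated at one dose or 18 have been enrolled in all. Table 5 plans two cohorts, 500 mg BID first and 375 mg BID below it.

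**The concern.** The statement is offered as a property of the design, and the only numbers beside it belong to the comparator. A reader cannot tell whether the table, used at 3 and then 6 or 9 patients, is more or less cautious than the 3+3.

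Appendix H says Stay at 2/6 and 3/6, outcomes at which a 3+3 does not keep the dose. No cohort above 500 mg is currently planned, so the decision this trial will mainly face is whether to keep 500 mg or reduce it. On that decision the table looks more permissive than the rule it is said to improve on.

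The Clinical Safety Committee (CSC) sets the recommended Phase 2 dose, and up to 75 patients may be treated in Phase 2. If the committee and ethics reviewers believe the rule is the more protective one, they may give a Stay recommendation more weight than its error rates justify.

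**Working it through.** **Inputs.** The review points are from Section 3.2.2. The Appendix H cells used are:
- n=3: 0 Escalate, 1 Stay, 2 De-escalate, 3 De-escalate/unacceptable.
- n=6: 0–1 Escalate, 2–3 Stay, 4 or more De-escalate/unacceptable.
- n=9: 0–1 Escalate, 2–4 Stay, 5 De-escalate, 6 or more De-escalate/unacceptable.

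Recomputing these cells with a uniform prior, the 28–38% interval and the 95% exclusion rule gives the same entries. The true DLT rates of 20% and 30% are those of Section 10.2.5; 40% and 50% are assumptions, chosen because they lie above the 28–38% interval.

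**Step 1: reproduce the plan's 3+3 figures.** Let p be the true DLT rate. If a dose passes at 0/3, or at 1/3 followed by 0/3, then

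P(pass) = (1−p)³ + 3p(1−p)² × (1−p)³.

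- p = 0.20: 0.512 + 0.384 × 0.512 = 70.9%.
- p = 0.30: 0.343 + 0.441 × 0.343 = 49.4%, and lower above that.

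Both stated figures reproduce, which fixes the 3+3 rule the plan has in mind.

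**Step 2: escalation under Appendix H.** With looks at 3 and 6, the table escalates at 0/3, or at 1/3 followed by 1/6. These are the 3+3 conditions, so the formula and the probabilities are identical. If six patients are added instead, escalation after 1/3 needs 0/6 more, and the last factor becomes (1−p)⁶. At p = 0.20 this gives 0.512 + 0.384 × 0.262 = 61.3%, below the 3+3.

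**Step 3: keeping the dose under Appendix H.** At n=3 the two rules agree: none passes, one adds patients, two or more go down. At n=6 the table keeps anything up to 3/6. After 0/3 the total cannot exceed 3/6; after 1/3 it exceeds 3/6 only if all three further patients have a DLT. So

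P(keep, n=6) = (1−p)³ + 3p(1−p)² × (1 − p³).

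- p = 0.40: 0.216 + 0.432 × 0.936 = 62.0%. The 3+3 gives 0.216 + 0.432 × 0.216 = 30.9%.
- p = 0.50: 0.125 + 0.375 × 0.875 = 45.3%. The 3+3 gives 0.125 + 0.375 × 0.125 = 17.2%.

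For n=9 the dose is kept at 4/9 or fewer:
- p = 0.40: 0.216 × 0.959 + 0.432 × 0.821 = 56.2%.
- p = 0.50: 0.125 × 0.891 + 0.375 × 0.656 = 35.7%.

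| True DLT rate | 3+3 passes (= mTPI escalates, n=6) | mTPI escalates, n=9 | mTPI keeps, n=6 (ratio to 3+3) | mTPI keeps, n=9 (ratio to 3+3) |
|---|---|---|---|---|
| 20% | 70.9% | 61.3% | 89.3% (1.26) | 88.9% (1.25) |
| 30% | 49.4% | 39.5% | 77.2% (1.56) | 74.9% (1.52) |
| 40% | 30.9% | 23.6% | 62.0% (2.01) | 56.2% (1.82) |
| 50% | 17.2% | 13.1% | 45.3% (2.64) | 35.7% (2.08) |

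**Step 4: other readings, at 40% and 50%.**
- If 3/6 cannot be selected, because 50% lies outside 28–38%, the dose is kept with probability 48.2% and 29.7% (ratios 1.56 and 1.73).
- Against a 3+3 that requires at most 1/6 in six patients (23.3% and 10.9%), the n=6 ratios are 2.66 and 4.14.

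**Step 5: Phase 1 exposure.** If both designs fill to six, expected patients at 500 mg are 3 + 3 × P(at most 1/3). That is 3 + 3 × 0.648 = 4.9 at 40% and 3 + 3 × 0.500 = 4.5 at 50%, the same for both. If six are added under the mTPI, the figures are 6.9 and 6.0.

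**The case against.** Several points on the other side have force.

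**The quantities are not alike.** Section 10.2.5 quotes the chance of escalation. On that measure this table equals 3+3 at looks of 3 and 6, and it escalates less often at 3 then 9. A reader might infer that the protective claim is simply reversed. The documents do not support that: on escalation the claim has no support at n=6 and some at n=9. The n=9 advantage has little to act on, however, while no dose above 500 mg is planned.

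**Retention is not exposure.** A reader might also infer that more Phase 1 patients will be treated above the MTD. Step 5 shows equal expected numbers if both designs fill to six. The mTPI treats more only if six patients are added, or if the 3+3 stops at 0/3.

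**No single factor is fixed.** Stay is an allocation decision, and Appendix H makes MTD selection a separate step at the end. Counting 3/6 as kept is therefore one reading, and the 2.0 and 2.6 should not be taken as settled. Part of the gap also follows from the target: a rule aimed at 33% will keep 2/6. That explains the permissiveness without making the comparative sentence true of this table.

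**The claim is generic and cited.** Section 3.2.2 speaks of the method, and Appendix H cites a published comparison that cannot be examined here. The check shows only that the property does not carry over to this set-up.

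**There are other safeguards.** The table is printed in full and only guides the CSC, which may meet at any time, decides on cumulative data and may add a safety expansion cohort. The early termination rule ("If there is greater than a 95% probability that toxicity with dose 1 is greater than the target toxicity level (33" percent) adds a stop, but the table's unacceptable code first appears at 3/3 and 4/6, so 3/6 remains Stay. These safeguards make harm less certain; they do not supply the missing error rates.

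**Conclusion.** The comparative statement in Sections 3.2.2 and 10.2.5 is not supported for the implementation planned here. The plan's own 3+3 arithmetic is correct, but it gives no evidence about the mTPI.

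On the decision to keep or reduce 500 mg, the table retains a dose above the target more often than 3+3 in every reading tried, with ratios from about 1.6 to 4.1 at assumed true rates of 40% to 50%. At n=6 the direction does not depend on the assumed rate: the table keeps every dose that the 3+3 of Section 10.2.5 keeps, and also some that it rejects.

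The result assumes that the CSC follows the table, that 500 mg remains the highest cohort, and that the 3+3 is the rule which reproduces the 71%. What is at stake is retention and possible carry-forward to Phase 2, not a demonstrated excess of Phase 1 exposure. The check does not judge which dose or decision rule is right.

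**What to change.** Delete or qualify the comparison with 3+3 in Sections 3.2.2 and 10.2.5. In its place, give a small table for the Appendix H rule at this trial's review points: the probability of escalating and of keeping the dose at true DLT rates of 20, 30, 40 and 50%, for n=6 and n=9. State whether 3/6 counts as keeping the dose, since the figures depend on it. If a 3+3 comparison is retained, show both rules on the same quantity.

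The cost is a change of wording in two sections and one short table. The dose, the decision table and the sample size are untouched. The downside is that the stated property becomes less favourable.

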3.2.3 Recommended Phase 2 Dose

The RP2D will be determined by the CSC based on cumulative data from all Dosing Cohorts in the Dose Finding Phase. A Safety Expansion Cohort of up to 6 patients may be enrolled to further examine the tolerability of a dose combination of interest or the tolerability of the combination dosing without a rociletinib Run-in-Period.

3.3 Dose Expansion Phase (Phase 2)

The Dose Expansion Phase will be conducted in two patient cohorts (see also Figure 1):

Group A: EGFR TKI treatment-naïve and chemotherapy-naïve patients.

Group B: Patients who have progressed after at least 12 weeks of treatment with a prior firstor second-generation EGFR TKI (ie, erlotinib, gefitinib, afatanib), regardless of T790M mutation status.

The Dose Expansion Phase will be used to assess the RP2D of the combination of rociletinib and MPDL3280A for preliminary efficacy and pharmacodynamics effects, in addition to safety and tolerability, in these patient populations. For the Dose Expansion Phase, there will not be a Run-in-Period; rather, treatment will begin with both rociletinib and MPDL3280A on Cycle 1 Day 1 (C1D1). Patients will receive daily oral BID doses of rociletinib (RP2D) and IV doses of MPDL3280A on Day 1 of each cycle, in consecutive 21-day cycles. Patients will be evaluated regularly for safety and efficacy according to the Schedule of Assessments (see Table 1). For further details on the planned assessments and analyses of safety, PK, efficacy and pharmacodynamics, please refer to Sections 8.4.2-8.4.5.

3.4 Study Conduct and Duration of Patient Follow-Up

The study will comprise a Screening Period, and Treatment Period, and a Follow-up Period as outlined in Table 6. Please refer to Section 8 for additional details.

	Sign ICF						
COFFNINC DEDIOD	Screening Assessments						
SCREENING PERIOD	Up to 28 days before 1st dose of study drug (biops	sy within 60 days pi	rior)				
	Enrollment						
	Study assessments every 21 days. Additional ECG and glucose		Day 1				
TREATMENT PERIOD	monitoring during Cycle 1 (Day 4, Day 8, and Day 15). Tumor	Cycle 1	Day 4				
Oral rociletinib BID + IV	assessments every 2 cycles through Cycle 6 (end of Cycles 2, 4, and 6): every 3 cycles after Cycle 6 (end of Cycles 9, 12, etc.); and	Cycle I	Day 8				
MPDL3280A every 21days	at the EOT Visit. The frequency of tumor assessments may be		Day15				
	reduced after 2 years with approval of Medical Monitor.	Cycle 2 +	Day 1				
		Ļ					
	Disease Progression	Rociletinib and	/or MPDL3280A				
		treatment post-progression (Spons					
	(Optional post-progression tumor biopsy)	approval) with con	rotocol				
		↓ .					
	Treatment discontinuation						
END OF STUDY PERIOD	Follow-up Safety Assessment						
	28 days after last dose of study drug (rociletinib or MPDL3280A)						
	PK/ATA blood samples 120 days after last dose of MPDL3280A (see Table 2)						
	Follow-up for subsequent anticancer therap	vies and survival					
	Every 12 weeks						

Table 6:Study Schematic (CO-1686-032)

ATA, anti-therapeutic antibody; BID, twice-daily; ICF, informed consent form; IV, intravenous; PK, pharmacokinetics

4 STUDY POPULATION

4.1 Number of Patients and Sites

The total enrollment planned for this study is approximately 93 patients (18 patients in Phase 1, and up to 75 patients in Phase 2). There will be approximately 14 investigative sites in the United States (US), France, and Spain.

4.2 Inclusion Criteria

All patients must meet all of the following inclusion criteria:

1. Signed and dated informed consent, approved by the Independent Ethics Committee (IEC) or Institutional Review Board (IRB), obtained prior to the performance of any study-specific procedures or assessments and ability to understand and comply with protocol requirements and instructions;

Baseline Characteristics

- 2. Males and females ≥ 18 years of age;
- 3. Eastern Cooperative Oncology Group (ECOG) performance status of 0 or 1;
- 4. Adequate hematological and biological function, based on the following laboratory values:
 - Bone Marrow Function
 - ANC $\geq 1.5 \times 10^{9}/L;$
 - Lymphocyte count $\geq 0.5 \times 10^9$ /L;
 - Platelets > 100.0 × 10⁹/L (without transfusion within 2 weeks prior to receipt of study drug);
 - Hemoglobin ≥ 9 g/dL (or 5.6 mmol/L) (patients may be transfused and/or receive erythropoietin stimulating agents to meet this criterion per institutional guidelines).
 - Hepatic Function
 - Aspartate aminotransferase (AST) and alanine aminotransferase (ALT)
 ≤ 2.5 × upper limit of normal (ULN); if liver metastases, ≤ 5 × ULN;
 - Bilirubin ≤ 2.0 × ULN (Patients with documented Gilbert's syndrome and conjugated bilirubin within the normal range may be allowed into the study. In this event, it will be documented that the patient was eligible based on conjugated bilirubin levels).
 - Renal Function
 - Serum creatinine $\leq 1.5 \times ULN$ or creatinine clearance $\geq 50 \text{ mL/min}$.

- Electrolytes
 - Potassium and magnesium within normal range, patients may receive supplements to meet this requirement.
- Coagulation status
 - International normalized ratio (INR) and activated partial thromboplastin time (aPTT) ≤ 1.5 × ULN;
 - This applies only to patients who are not receiving therapeutic anticoagulation; patients receiving therapeutic anticoagulation should be on a stable dose.
- 5. Ability to swallow and retain orally administered study drug;

EGFRm NSCLC Disease Characteristics

- 6. Histologically or cytologically documented metastatic or unresectable, locally advanced or metastatic NSCLC, with prior histopathological reports showing evidence of one or more activating EGFR mutation (eg, G719X, exon 19 deletion, L858R, L861Q), except for exon 20 insertion;
- 7. Measurable disease as defined by RECIST v1.1 (Appendix A):
 - Previously irradiated lesions should not be counted as target lesions;
 - Lesions that are intended to be used to collect tissue samples for biopsy should not be counted as target lesions.
- 8. Biopsy of tumor tissue for central evaluation within 60 days prior to the first day of study treatment (Run-in-Period Day 1 for Phase 1; C1D1 for Phase 2);
- 9. For Phase 1 and Phase 2 Group B, patients must have progressed after at least 12 weeks of treatment with a 1st or 2nd generation EGFR TKI (eg, erlotinib, gefitinib, afatinib) for advanced or metastatic NSCLC. A minimum of a 3-day washout period is required for previous EGFR TKIs.
 - Previous chemotherapy for NSCLC is allowed for patients enrolled in Phase 1 and Phase 2 Group B.
- 10. For Phase 2 Group A, patients must be EGFR TKI treatment-naïve and chemotherapy-naïve;
- 11. Anticipated life expectancy of at least 3 months;

Medical/Surgical History

- 12. A minimum of 14 days must have elapsed since any palliative radiotherapy;
- 13. A minimum of 14 days must have elapsed from last invasive surgery, and wound healing has occurred;
- 14. Any ongoing potentially reversible treatment-related toxicities must be resolved to Grade ≤ 1 EXCEPT alopecia or (with agreement from the Medical Monitor) the expected EGFR TKI toxicities of rash or diarrhea that are stable with intervention;
- 15. No planned major surgery while on study;

Concomitant Medications or Procedures

- 16. Women of childbearing potential must have a negative serum pregnancy test within 7 days prior to the first dose of study treatment and agree to use highly effective contraception as defined in the full protocol, during the study and for 90 days following the last dose of MPDL3280A or rociletinib;
- 17. Men with a female partner of childbearing potential must have either had a prior vasectomy or agree to use effective contraception as described in the full protocol for at least 14 days prior to administration of the first dose of study treatment, during the study, and for 90 days following the last dose of MPDL3280A or rociletinib.

